2.3.2 Known Potential Benefits

Families in the intervention arm will be provided with toothbrushes and toothpaste supplied at regular intervals to meet the needs of all family members throughout the study. Families in the usual care arm will also receive toothbrushes and toothpaste after the completion of each annual survey. All participating children will receive a thorough oral health screening, a service not always available. If a child is found to have a dental emergency, e.g., a dental abscess, he/she will be immediately referred to the Head Start teacher, who has procedures in place for managing medical emergencies.

The study will provide knowledge to potentially allow for the development and implementation of an effective oral health program for the prevention of ECC in rural AI populations.

3 OBJECTIVES

3.1 Study Objectives

3.1.1 Primary:

3.1.1.1 To develop, with the input from tribal/community members, a manualized intervention protocol for an ECC prevention program for delivery by specially trained community paraprofessionals, called Community Oral Health Specialists (COHS)

3.1.1.2 To implement and evaluate the delivery of FV and OHP programs in AI Head Start Centers under the following conditions:

Group 1 - FV (offered 4x a year) and OHP for 2 years by specially trained COHS; toothbrushes and toothpaste supplied for entire family

Group 2 - Usual oral health care made available by their usual dental providers, usually IHS; toothbrushes and toothpaste supplied for entire family

3.1.1.3 To assess efficacy by comparing dmfs over time between the two groups

3.1.2 Secondary:

3.1.2.1 To assess specific caries patterns

3.1.2.2 To investigate moderators/mediators of the intervention conditions as ascertained via questionnaires on knowledge, attitudes, and behaviors

3.1.2.3 To investigate participant utilization of medical and dental services for oral health problems and intervention costs, intervention savings, net intervention costs, costs/net costs per participant, costs/net costs per unit decrease in caries associated with each intervention condition

3.2 Study Outcome Measures

3.2.1 Primary Outcome Measure

Decayed, missing, and filled primary tooth surfaces (dmfs) of the children in the study at baseline, and annually for 3 years.

3.2.2 Secondary Outcome Measures

- 3.2.2.1 Dental caries patterns (anterior, facial/lingual, molar, fissure caries, demineralization, etc.)
- 3.2.2.2 Variables that may serve as moderators/mediators of the intervention conditions as ascertained via questionnaires on knowledge, attitudes, and behaviors
- 3.2.2.3 Participant use of dental and health services for oral health problems, program costs associated with each intervention condition, net program costs, costs per participant, costs of caries and caries averted

4 STUDY DESIGN

This is a multicenter, Phase IV, cluster randomized trial to determine whether an intensive intervention of COHS's administering FV (offered 4x a year) and OHP for 2 years in an AI population of children ages 3-6 years in HSCs on the Navajo Reservation vs. usual oral health care made available by the IHS dental providers will reduce the dmfs measure in the children. A cluster randomized design was chosen to reduce the potential for contamination between the 2 intervention groups.

There are approximately 96 HSC classrooms in the NN (based on 2011-2012 school year). We will stratify HSCs on the basis of population size, and randomly assign the HSC classrooms to the 2 arms of the study within the strata. This will make the number of children in each of the 2 arms of the study approximately equal.

The intensive intervention group will have the specially-trained COHS administer FV to the children 4x a year and provide OHP to the parents/caregivers and to the children in the HS classrooms, for 2 years. The other randomized group will have usual oral health care made available by the IHS Dental providers or other community providers.

Enrollment of HSCs will be done over a period of 6 months (in each year, year 1 and year 2). Upon parental consent of the child and parent/primary caregiver consent for her/himself, the HS children from each HSC classroom will be enrolled in the study. Each consented child will participate in the study for up to 3 years. A baseline assessment of the dmfs measure for each child will be done (objective 3.1.1.3 and 3.1.2.1/ outcome 3.2.1 and 3.2.2.1), and a baseline assessment of the dental knowledge, attitudes, and behaviors of the parents/caregivers (objectives 3.1.2.2 and 3.1.2.3/ outcome 3.2.2.2 and 3.2.2.3). The interventions will be administered for 2 years in the Head Start classrooms. The number of interventions a participating child receives will vary with the length of time that the child attends the Head Start class. Annual assessments of the dmfs measure for the children and the dental knowledge, attitudes, and behaviors of the parents/caregivers will be made for 3 years. The 3rd annual assessment is included to determine changes in the outcome measures for up to 18 months after the FV and OHP have ended, to assess the longer term effects of the intervention.

The primary outcome of the study will be changes from baseline in dmfs (dmfs increment at two and three years) between the 2 groups. Secondary outcomes will include possible changes in caries patterns, and potential moderators/mediators of treatment effect such as parental knowledge, attitudes and behaviors, and the cost of each of the two intervention conditions.

The dmfs measures (objective 3.1.1.3 and 3.1.2.1/ outcome 3.2.1 and 3.2.2.1) will be made by oral screening of the children, to be completed by calibrated dental hygienists who will visit each HSC in both the COHS intervention (Group 1) and the Usual Care (Group 2) arms.

Questionnaires, known as the Basic Research Factors Questionnaire (BRFQ) or Audio Computer Assisted Survey Interview (ACASI) survey, of dental knowledge, attitudes, behaviors and service utilization (objectives 3.1.2.2 and 3.1.2.3/ outcome 3.2.2.2 and 3.2.2.3) will be completed by the parents/caregivers annually, and the data will be entered into laptop computers. We will follow the families whose children age out of Head Start and make arrangements for them to complete the child oral health screening and parent questionnaires at a convenient time and location. All data collected on laptops in the field will be sent first to UCD and then uploaded to the central statistical coordinating center.

NIDCR has appointed a Data Safety and Monitoring Board to provide oversight of the studies and review of interim analyses for all ECC projects in the consortium.

A Manual of Procedures (MOP) has been created to detail the conduct and operations of the study. It transforms the study protocol into a guideline that describes all aspects of the study's organization, operational definitions, recruitment, screening, enrollment, randomization, intervention, follow-up procedures, data collection methods, data tracking and transfer, case report forms (CRFs), and quality control procedures.

The MOP is a dynamic document that will be updated throughout the study to reflect any amendments to the protocol, participant consent forms, CRFs and study procedures. The MOP will be submitted once a year at continuing review unless it requires a change in the protocol. At continuing review, tracked changes and a summary of updates to the MOP made throughout the year will be submitted.

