14.1	Data Management Responsibilities	46
14.2	Data Capture Methods.....	46
14.3	Types of Data.....	47
14.4	Timing/Reports.....	47
14.5	Study Records Retention	47
14.6	Protocol Violations/ Reportable Events.....	47
15	Publication Policy.....	49
16	Literature References	50
17	APPENDICES.....	52

LIST OF ABBREVIATIONS

ACASI	Audio Computer Assisted Survey Interview
AE	Adverse Event
AI	American Indian
AI/AN	American Indian/Alaska Native
BRFQ	Basic Research Factors Questionnaire (referred as ACASI survey)
CHRs	Community Health Representatives
CNOHR	Center for Native Oral Health Research
COHS	Community Oral Health Specialist
COMIRB	Colorado Multiple Institutional Review Board
CTCAE	Common Terminology Criteria for Adverse Events
dmfs	Decayed, missing and filled tooth surfaces index (primary)
DSMB	Data and Safety Monitoring Board
ECC	Early Childhood Caries
FV	Fluoride Varnish
HIPAA	Health Information Portability and Accountability Act
HRSA	Health Resources and Services Administration
HS	Head Start
HSCs	Head Start Centers
IHS	Indian Health Service
MAR	Missing at Random
MCAR	Missing Completely at Random
MNAR	Missing Not at Random
MOP	Manual of Procedures
NHANES	National Health and Nutrition Examination Survey
NIDCR	National Institute of Dental and Craniofacial Research
NN	Navajo Nation
NNHRRB	Navajo Nation Human Research Review Board
OHP	Oral Health Promotion
PI	Principal Investigator
RDHs	Registered Dental Hygienists
SA	Specific Aim
SAE	Serious Adverse Event
SODM	School of Dental Medicine
UCD	University of Colorado Anschutz Medical Campus
UP	Unanticipated Problems

PROTOCOL SUMMARY

Title:	Preventing Caries in Preschoolers: Testing a Unique Service Delivery Model in American Indian Head Start Programs
Phase:	IV
Population:	Children ages 3-6 years in Head Start (HS) Programs in the Navajo Nation (NN)
Number of Sites:	3 (Navajo Nation, University of Colorado Anschutz Medical Campus, University of California San Francisco)
Study Duration:	The study duration will be 6 years. This includes 1 year for planning, 6 months for each intervention year (1 & 2) for recruitment, 3 years for implementation of the interventions: baseline and follow-up evaluations, and 1 year for close-out and analysis.
Subject Participation Duration:	Each participant will be in the study for up to 3 years; 2 years of intervention and a third year for follow up measures.

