Description of Agent or Intervention:	Intervention will include application of fluoride varnish (FV) offered offered 4x a year and oral health promotion (OHP) and education for 2 years.
Objectives:	
Primary:
 
1) To develop, with input from tribal/community members, a manualized intervention protocol for an early childhood caries (ECC) prevention program to be delivered by specially trained community paraprofessionals, called Community Oral Health Specialists (COHS)2) To implement and evaluate the delivery of FV and OHP programs in American Indian (AI) Head Start Centers (HSCs) under the following conditions: Group #1—FV offered 4x a year and OHP for 2 years provided by COHS Group #2— Usual oral health care made available by the IHS Dental providers (or other usual providers)3) To assess efficacy by comparing decayed, missing, and filled

primary tooth surfaces (dmfs) over time between the 2 groups.

Secondary:

- 1) To assess specific caries patterns
- 2) To investigate moderators/mediators of the intervention conditions as ascertained via questionnaires on oral health knowledge, attitudes, and behaviors
- 3) To investigate participant utilization of medical and dental services for oral health problems and intervention costs, intervention savings, net intervention costs, costs/net costs per participant, costs/net costs per unit decrease in caries associated with each intervention condition

[figure not shown]
**Description of Study
Design:**

The study design will be a cluster randomized design. HSCs within the Navajo Nation (NN) will be stratified by population size and randomized within strata to the two groups. All children within the HSC classrooms and a parent/primary caregiver of each child will be invited to participate in the intervention condition to which the HSC is randomized. Children will participate after informed consent by the parents and after informed consent by the participating parent/primary caregiver for her/himself. To be consistent with NIDCR, we will count the child and participating parent/primary caregiver dyad as one enrolled participant (unit). Baseline and annual measures of dmfs and of dental knowledge, attitudes, and behavior will be collected. Changes in these outcome measures will be compared between the two groups.

**Estimated Time to
Complete Enrollment:**

6 months for each intervention year (year 1 and year 2)

Schematic of Study Design:

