10.2 Sample Size Considerations

Sample size is based upon the following assumptions:

1. The primary outcome measure is dmfs, measured at baseline and annually for three years after the beginning of the intervention when the HS children ages 3-5 at enrollment (or possibly 6, depending on the timing of enrollment) will be ages 6-8 (or possibly 9).
2. The test statistic used is the t-test for 2 independent samples, with an inflation factor for the cluster randomized design.^{29, 30}
3. The null hypothesis is no difference in the mean dmfs between the 2 randomized groups 2 years and 3 years after the beginning of the intervention when the children are 5-7 6-8 (or possibly 9) years old. The alternative hypothesis is that there is a difference.
4. Type I error rate will be set at 0.05
5. Type II error rate will be set at 0.20 (Power = 0.80)
6. From the 1999 IHS oral health survey ⁵, the average dmfs for AI children ages 5-7 was 18.55. It was also observed that Navajo children tended to have dmfs measures about 30% higher than the national average for all AI children. Therefore, it was assumed that the average dmfs for Navajo children ages 5-7 will be about 24 under conditions of usual care, with a standard deviation of about 24. We also assumed a 40% reduction in this average dmfs measure for group 1.
7. Based on the experience of other studies the Centers for American Indian and Alaska Native Health have conducted with AI communities, a 70% retention rate was assumed.

8. If subjects drop out of the study due to adverse effects or other reasons, we will ask them to continue in the follow-up even if treatment is discontinued, so that we can perform an “intention to treat” analysis. The “intention to treat” analysis will be the primary analysis of the study.
9. We also assumed an average HS class size of about 20 children and an intraclass correlation of about 0.045, considered to be an appropriate intraclass correlation.³¹

On the basis of the assumptions above, we calculate a need to randomize 52 HSC classrooms, or about 26 HSC classrooms in group 1 and 26 HSC classrooms in group 2. This means that we will need to enroll about 1040 children, or 520 children in group 1 and 520 children in group 2. Sample size calculations are shown in the table in *Appendix B*.

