10.4 Final Analysis Plan

The primary outcome measure will be the difference between groups 1 and 2 on the changes in mean dmfs between baseline and 2-year and 3-year follow-up. Descriptive statistics will be examined first to yield important information about the most appropriate analysis strategies. If the change scores for dmfs are not normally distributed, a log transformation can be made, or a non-parametric test can be used. Longitudinal methods of analysis will be used to examine these repeated, correlated observations within subjects over time.^{32, 33} Other models such as negative binomial regression, mixture models such as ZIP and ZINB will be considered.

Exploratory analyses will first be done to evaluate the trends in the data to determine the most appropriate mean and covariance structures for the data. Graphical displays will be used to assess the mean structure for modeling fixed effects, including scatter plots of the response variable versus time, plots of individual subject profiles, plots of mean profiles, and smooth curve fits to the data. Simple plots of individual subject profiles (dmfs over time) can be very revealing and show whether there is heteroscedasticity in the data (fanning of the curves with time).

Linear mixed models will be used because they can incorporate both fixed and random (subject-specific) effects and permit different covariance structures. A typical example (“random regression”) allows each subject an individual time trend, and treatment effects may cause differences in slope over time. The within-subjects autocorrelation is assumed to be due to these individual trends, on top of which is superimposed independent measurement errors. When analyzing randomized trials, it is assumed that the responses are the values that occur after randomization, because they are influenced by treatment. Thus, it is customary in such trials to consider the baseline value as a covariate, rather than as a response variable. The randomization of subjects in groups or clusters (i.e., HSCs) can also be accounted for in the mixed model with a random effect for group.

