Two important considerations in fitting mixed models are determining covariance and mean structures for the data. We will first define the covariance structure; many forms are available, depending on the correlations in the data. Little, et al.,³⁴ provide a useful article on modeling the covariance structure for longitudinal data by using the MIXED procedure in SAS software. Once a suitable covariance structure has been determined, an appropriate mean structure can be determined.

Missing or incomplete data are a common problem in randomized clinical trials where the outcome is measured longitudinally. Here, exploratory analyses will be done first to determine if the missing observations are missing completely at random (MCAR), missing at random (MAR), or missing not at random (MNAR) and whether multiple imputation should be done, or modeling of the non-response. Complete case analysis will be the primary analysis,

since available data analysis with mixed models only assumes MAR (Molenberghs). As a secondary analysis multiple imputation or modeling of the non-response mechanism will be done to include those cases without complete data.

The secondary outcomes will include caries patterns, cost analyses and the array of information representing knowledge, attitudes, and behaviors of parents that may serve as mediating and moderating variables. Caries patterns will be analyzed by looking at the different dmfs components and the specific teeth involved.

Cost-effectiveness analysis is used to compare costs of alternative interventions for a similar health outcome. Results are presented as a cost-effectiveness (or CE) ratio of the intervention net cost (intervention costs minus savings) per health outcome such as improvement in quality-adjusted life years (QOL). For this proposal, intervention cost and net cost estimates will be used to construct cost indicators such as the cost/net cost per child served and, if the program is found to be effective, the cost/net cost per unit decrease in caries. Such indicators are sometimes referred to as preliminary CE ratios for 2 reasons. First, the ratios measure the cost for a process-outcome or a health-outcome such as caries rather than QOL. Second, we will estimate only short-term net intervention costs, not long-term costs that may result with improvements in oral health behaviors and practices overtime.

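### Children enrolled in intervention year 2 may have no 3-year visit, and a literal complete-case primary analysis would drop them for it

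*Combined protocol and SAP*

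**What the plan says.** **Recruitment and field phase.** The Protocol Summary allots "6 months for each intervention year (1 & 2) for recruitment, 3 years for implementation of the interventions: baseline and follow-up evaluations". Section 4 likewise has centres enrolled over six months in each of years 1 and 2.

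**Participation and exposure.** The Summary says "Each participant will be in the study for up to 3 years; 2 years of intervention and a third year for follow up measures". Section 4 says "Each consented child will participate in the study for up to 3 years" and adds "The number of interventions a participating child receives will vary with the length of time that the child attends the Head Start class". It places the third annual assessment at most 18 months after the intervention ends.

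**Number of screenings.** Section 8.1 gives a maximum of four per child. Section 14.4 promises every child a baseline screening and three years of annual ones, and Section 7.3 also describes three annual measures.

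**Clock.** Section 10.2 has dmfs "measured at baseline and annually for three years after the beginning of the intervention". Section 10.4 defines the primary outcome through "changes in mean dmfs between baseline and 2-year and 3-year follow-up", and Section 4 also counts from baseline.

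**Retention and analysis.** Section 10.2 assumes 70% retention, stated once for all children and both time points, and makes intention to treat primary. Section 10.4 plans linear mixed models and then says "Complete case analysis will be the primary analysis", on the ground that a mixed model on available data needs only missing at random (MAR). Multiple imputation or non-response modelling is secondary. Enrolment year is not mentioned in Section 10.2 or 10.4.

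**The concern.** Recruitment continues into the second year of a two-year programme, but the endpoint, the retention rate and the missing-data rule are each written as if all children start together. For a year-1 enrollee, time since the start of the intervention and time since baseline roughly agree. For a year-2 enrollee they differ by about a year, so Sections 10.2 and 10.4 point to different visits.

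If the third visit of year-2 enrollees falls outside the field phase, it is absent by design rather than through dropout. A complete-case rule does not make that distinction. The primary 3-year result would then describe year-1 enrollees only, children with usable earlier visits would be set aside, and the 70% retention assumption would not describe the 3-year sample. That works against the intention-to-treat aim in Section 10.2.

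**Working it through.** **1. The plan's own figure.** Inputs from Section 10.2: mean 24, SD 24, 40% reduction (0.40 × 24 = 9.6), alpha 0.05 (two-sided, as implied), power 0.80, class size 20, ICC 0.045, retention 70%.

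- Unadjusted: 2 × (1.960 + 0.842)² × 24² / 9.6² = 98.1, so 99 per arm.
- Design effect: 1 + 19 × 0.045 = 1.855; 99 × 1.855 ≈ 184.
- Retention: 184 / 0.70 ≈ 263 per arm, about 525 in total.

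The protocol states 520 per arm and 1040 in total, so its figure is not reproduced. The Appendix B table is not in the text available, and the discrepancy is a separate matter. The steps below take 1040 as given.

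**2. The calendar.** Assume one programme running from month 0 to month 24, with recruitment in the first six months of each year.

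- Year-1 enrollees enter at months 0 to 6. Their third annual visit falls at months 36 to 42, which is 12 to 18 months after the programme ends. This matches the 18-month limit in Section 4.
- Year-2 enrollees enter at months 12 to 18, with 12 to 6 months of programme left. Their third annual visit would fall at months 48 to 54, which is 24 to 30 months after the end.
- Section 10.2 expects children aged 3-5 at enrolment to be 6-8 three years after the intervention begins. A child who enters at 3-5 a year later would then be about 5-7.
- Section 8.4.2 describes two years of treatment and one further year of follow-up.

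These passages fit year-1 enrollees, but they do not prove a single calendar. A clock that restarts when a centre enters would also satisfy the 18-month limit. The Summary's six years add up as 1 + 2 × 0.5 + 3 + 1 only if recruitment lies outside the three field years, in which case a year-2 child's third visit might fit.

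**3. Size if year-2 enrollees have no 3-year visit.** Their share f is not in the documents; 20%, 30% and 50% are assumed. With f = 0 there are 1040 × 0.70 = 728 completers, or 20 × 0.70 = 14 per classroom.

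- Completers: 728 × (1 − f). Effective retention: 0.70 × (1 − f).
- Interval width if losses are spread within the 52 classrooms: the variance is proportional to [1 + (m − 1) × 0.045] / m, with m = 14 × (1 − f). At m = 14 this is 1.585 / 14 = 0.1132. At m = 11.2, 9.8 and 7 it is 0.1303, 0.1424 and 0.1814. The square roots of the ratios are 1.07, 1.12 and 1.27.
- Interval width if whole classrooms are lost: 1/√(1 − f).
- Power at the stated 40% effect: Φ(9.6 / [24 × √(2 × 1.855 / n)] − 1.96), with n = 364 × (1 − f) per arm. Keeping 1.855 is cautious, because smaller clusters lower the design effect.

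| f | 3-year completers | Effective retention | Wider, losses spread | Wider, whole classrooms lost | Power |
|---|---|---|---|---|---|
| 0 | 728 | 70% | – | – | 98% |
| 20% | 582 | 56% | 7% | 12% | 94% |
| 30% | 510 | 49% | 12% | 20% | 91% |
| 50% | 364 | 35% | 27% | 41% | 80% |

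**4. Sensitivity.** If 520 per arm were instead exactly the number for 80% power (which back-solves to a 28% reduction), 3-year power would be 71%, 65% and 51%. The stated inputs do not imply this.

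**The case against.** The strongest reply is that the missing visit is inferred. Section 14.4 promises all children three years of screening, Section 4 speaks of enrolling centres (which could each start their own two years), and the duration arithmetic leaves room for a longer field phase. The Manual of Procedures, not among the documents here, may settle it. This stands: a reader might conclude that year-2 enrollees cannot receive the full programme and have no 3-year visit, and the documents do not establish that. They leave it open and contradict themselves.

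Other tempting readings also fail:

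- *A year-2 child's 24-month visit would be pooled as a 3-year result.* Nothing relabels it. Sections 4 and 10.4 define change from baseline, and Section 7.3 ties visits to anniversaries of the previous screening at the centre.
- *The comparison is biased.* A visit absent because of the calendar is absent in both arms. No difference between arms is shown.
- *The trial is underpowered, or its effect diluted by a known amount.* Power holds on the stated inputs, and the documents give no relation between exposure and effect. Variable exposure is disclosed and compatible with intention to treat.
- *The 2-year increment should become the sole primary endpoint.* That is a trade-off, since Section 4 includes the third assessment to study longer-term effects.

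It can also be said that Section 10.4 may intend the available-data mixed model all along. The sentence is ambiguous, and the reason it gives supports the analysis it appears to set aside. It also does not define a complete case. If completeness is judged separately at each time point, only the 3-year contrast loses these children; if all visits are required, the 2-year contrast loses them too.

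**Conclusion.** The point holds as a conditional one. The protocol does not settle whether year-2 enrollees have a 3-year visit, uses two clocks, applies one retention rate to everyone, and names a primary analysis that, read literally, would exclude children for an unscheduled visit.

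If the visit is absent and 20% to 50% of children enrol in year 2 (an assumed range), effective 3-year retention is 56% to 35% rather than 70%. Intervals are about 7% to 27% wider with losses spread across classrooms, and up to 12% to 41% wider if whole classrooms go. If every child has a 3-year visit, none of this loss arises, and what remains is the inconsistent wording and the choice of complete case. The main harm is an unclear 3-year target population and an avoidable exclusion, not loss of power or demonstrated bias.

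**What to change.** 1. In Section 10.4, make the planned linear mixed model primary, with a random effect for centre and baseline dmfs as covariate, fitted to all available post-baseline visits. Keep complete case as a sensitivity analysis. Children without a 3-year visit then still contribute their earlier visits.
2. In Section 10.2, count time from each child's own baseline, as Section 10.4 already does.
3. Reconcile the Protocol Summary and Sections 4, 8.1 and 14.4 on whether year-2 enrollees have a 3-year visit.
4. If they do not, restate in Section 10.2 the expected numbers and retention at 2 and 3 years.

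The cost is wording, a short recalculation, minor analysis work and a somewhat less favourable 3-year figure. The mixed model still rests on MAR: year-2 enrollees' unobserved 3-year outcomes must be predictable from their observed visits under the fitted model. The imputation or non-response modelling already planned in Section 10.4 can be used to examine this.
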